5.1 Study Design

Study B020 is designed as a retrospective cohort study evaluating data for patients presenting with ACS managed with a PCI from 8 academic centers in the US from 01 January 2010 to 30 June 2013, with any follow-up data available for analysis. The centers include: Mount Sinai Medical Center, Intermountain Heart Institute, Duke University, Cleveland Clinic Foundation, University of Pittsburgh, University of Minnesota, Christiana Health Care and Aurora Research Institute. This study will evaluate the comparative effectiveness and economics of a treatment strategy initiating prasugrel relative to clopidogrel in approximately 8,600 patients (minimum 4,300 receiving prasugrel) in a usual care environment from academic centers in the US. These academic centers maintain institutional databases related to baseline characteristics, procedural characteristics, and clinical and economic outcomes during and following index hospitalization of patients with ACS undergoing PCI.

The participating academic centers will run a query in their ACS-PCI database to identify all patients who received prasugrel or clopidogrel between 01 January 2010 and 30 June 2013. The study period was selected based on the approval and availability of prasugrel in the US market at the end of 2009 and by the need for a study with a minimum 90-day follow-up in this population. The primary endpoint of the study will be at 90 days from index PCI; at this point in therapy, the adherence rate is expected to continue to be high while the switching rate is expected to be low ($\leq 10\%$). Figure 1 illustrates the study time periods

[figure not shown]

Figure 1 Study B020 design for patients with ACS managed with PCI and treated with prasugrel or clopidogrel between 01 January 2010 and 30 June 2013.

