Propensity scores will be calculated using a multivariable logistic regression model with the dependent outcome as treatment initiation with prasugrel (versus clopidogrel). In addition to age, and gender, this model will include all baseline covariates demonstrating significant differences ($p < 0.05$) between groups. Additional variables for which there is consensus that may be related to either the outcome or exposure will also be included as covariates, even in the absence of significant baseline differences between groups. From this logistic regression model, each observation will be assigned a predicted probability for prasugrel treatment. Baseline characteristics including calculated propensity score will be reviewed to better understand the data and specified analyses plan for the outcomes (stratification, matching, IPW, and etc) will be finalized and documented prior to any actual analyses on the outcomes. The distribution of propensity scores for the entire cohort and each treatment group will be visually examined. Mutually exclusive strata will then be generated based on the propensity scores for the entire cohort, a process which will be blinded to any outcome data in order to avoid bias in selection. The number of strata and their respective cut-points will not be defined *a priori* but will be based on fulfilling the following criteria:

1. Sufficient number of strata to ensure adequate bias adjustment (i.e. at least 5 strata) [Rosenbaum et al., 1984];
2. Sufficient proportion of prasugrel and clopidogrel patients (at least 3%) within each stratum to allow reliable risk estimation [D'Agostino et al., circulation 2007];
3. Adequate balance in baseline covariates will be assessed by calculating the standardized differences between exposure groups within strata for the following variables: age, gender, serum creatinine, serum hemoglobin and prevalence of DM. A standardized difference exceeding 10% will be considered as inadequate bias adjustment..
4. Individuals with an extremely high or low propensity for prasugrel, defined as propensity scores exceeding the 95th or below the 5th percentile for the

entire cohort, may be removed from the analysis of the primary MACE endpoint (i.e. trimming).

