8.1 Demographic and Baseline Variables

For each center the variables listed in the table in the section 12 Listing of Tables, Listings, and Figures will be considered as demographic or baseline variables.

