Min , Max	x.xx,x.xx	x.xx,x.xx	x.xx,x.xx	
Ethnicity		xx (x.x%)	xx (x.x%)	x.xxx
Hispanic	xx (x.x%)	xx (x.x%)	xx (x.x%)	
Non-Hispanic	xx (x.x%)	xx (x.x%)	xx (x.x%)	
Race				
African American	xx (x.x%)	xx (x.x%)	xx (x.x%)	x.xxx
White	xx (x.x%)	xx (x.x%)	xx (x.x%)	x.xxx
Other	xx (x.x%)	xx (x.x%)	xx (x.x%)	x.xxx
Diabetes at baseline	xx (x.x%)	xx (x.x%)	xx (x.x%)	x.xxx
Insulin-requiring diabetes at baseline	xx (x.x%)	xx (x.x%)	xx (x.x%)	x.xxx
Hypertension	xx (x.x%)	xx (x.x%)	xx (x.x%)	x.xxx
Hypercholesterolemia	xx (x.x%)	xx (x.x%)	xx (x.x%)	x.xxx
Pre-Procedure Creatinine, mg/dl				x.xxx
N, N Missing	xxx,x	xxx,x	xxx,x	
Mean ± Std	x.xx ± x.xx	x.xx ± x.xx	x.xx ± x.xx	
Median	x.xx	x.xx	x.xx	
Min , Max	x.xx,x.xx	x.xx,x.xx	x.xx,x.xx	
Pre-Procedure Hemoglobin, mg/dl				x.xxx
N, N Missing	xxx,x	xxx,x	xxx,x	

Table 1. Summary of Baseline Characteristics by Therapy at PCI.

	Overall (N = XX)	Prasugrel XX (XX%)	Clopidogrel XX (XX%)	Pvalue
Mean ± Std	x.xx ± x.xx	x.xx ± x.xx	x.xx ± x.xx	
Median	x.xx	x.xx	x.xx	
Min , Max	x.xx,x.xx	x.xx,x.xx	x.xx,x.xx	
Troponin				x.xxx
N, N Missing	xxx,x	xxx,x	xxx,x	
Mean ± Std	x.xx ± x.xx	x.xx ± x.xx	x.xx ± x.xx	
Median	x.xx	x.xx	x.xx	
Min , Max	x.xx,x.xx	x.xx,x.xx	x.xx,x.xx	
Baseline CK-MB, ng/ml				x.xxx
N, N Missing	xxx,x	xxx,x	xxx,x	
Mean ± Std	x.xx ± x.xx	x.xx ± x.xx	x.xx ± x.xx	
Median	x.xx	x.xx	x.xx	
Min , Max	x.xx,x.xx	x.xx,x.xx	x.xx,x.xx	
Peak serum creatinine, mg/dl				x.xxx
N, N Missing	xxx,x	xxx,x	xxx,x	
Mean ± Std	x.xx ± x.xx	x.xx ± x.xx	x.xx ± x.xx	
Median	x.xx	x.xx	x.xx	
Min , Max	x.xx,x.xx	x.xx,x.xx	x.xx,x.xx	
Nadir hemoglobin, g/dl (lowest within 72 hours)				x.xxx
N, N Missing	xxx,x	xxx,x	xxx,x	
Mean ± Std	x.xx ± x.xx	x.xx ± x.xx	x.xx ± x.xx	
Median	x.xx	x.xx	x.xx	
Min , Max	x.xx,x.xx	x.xx,x.xx	x.xx,x.xx	
Peak CK-MB, ng/ml (highest 6-24 hours after PCI)				x.xxx
N, N Missing	xxx,x	xxx,x	xxx,x	
Mean ± Std	x.xx ± x.xx	x.xx ± x.xx	x.xx ± x.xx	
Median	x.xx	x.xx	x.xx	
Min , Max	x.xx,x.xx	x.xx,x.xx	x.xx,x.xx	
Peak Troponin (highest 6-24 hours after PCI)				x.xxx
N, N Missing	xxx,x	xxx,x	xxx,x	
Mean ± Std	x.xx ± x.xx	x.xx ± x.xx	x.xx ± x.xx	
Median	x.xx	x.xx	x.xx	
Min , Max	x.xx,x.xx	x.xx,x.xx	x.xx,x.xx	
Smoking	xx (x.x%)	xx (x.x%)	xx (x.x%)	x.xxx
ISCHEMIC HISTORY				
Family history of CAD	xx (x.x%)	xx (x.x%)	xx (x.x%)	x.xxx
Previous MI	xx (x.x%)	xx (x.x%)	xx (x.x%)	x.xxx
Previous PCI	xx (x.x%)	xx (x.x%)	xx (x.x%)	x.xxx

Table 1. Summary of Baseline Characteristics by Therapy at PCI.

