Hypertension	0=no, 1=yes	Hypertension is defined by any one of the following: 
 • History of hypertension diagnosed and treated with medication, diet and/or exercise • Prior documentation of blood pressure greater than 140 mm Hg systolic and/or 90 mm Hg diastolic for patients without diabetes or chronic kidney disease, or prior documentation of blood pressure greater than 130 mm Hg systolic and/or 80 mm Hg diastolic on at least two occasions for patients with diabetes or chronic kidney disease • Currently on pharmacologic therapy for treatment of hypertension.
Hypercholesterolemia	0=no, 1=yes	Indicate if the patient has a history of dyslipidemia diagnosed and/or treated by a physician. Target Value: Any occurrence between birth and arrival at this facility Dyslipidemia: National Cholesterol Education Program criteria include documentation of the following: 
 A. Total cholesterol greater than 200 mg/dL (5.18 mmol/l); or B. Low-density lipoprotein (LDL) greater than or equal to 130 mg/dL (3.37 mmol/l); or, C. High-density lipoprotein (HDL) less than 40 mg/dL (1.04 mmol/l). For patients with known coronary artery

		disease, treatment is initiated if LDL is greater than 100 mg/dL (2.59mmol/l), and this would qualify as hypercholesterolemia
Serum creatinine	in mg/dl	Pre-procedure value
Serum hemoglobin	in g/dl	Pre-procedure value
Troponin		Pre-procedure value
CK-MB baseline	ng/ml	Pre-procedure value
Peak serum creatinine	in mg/dl	highest value; leave missing if not drawn
Nadir hemoglobin	in g/dl	lowest within 72 hours;. leave missing if not drawn
Peak CK-MB	ng/ml	highest 6-24 hours; leave missing if not drawn
Peak Troponin		highest 6-24 hours; leave missing if not drawn
Smoking	0=no, 1=yes	Indicate if the patient has smoked cigarettes anytime during the year prior to arrival Coding Instructions: at your facility. Target Value: Any occurrence between 1 year prior to arrival at this facility and arrival at this facility
Family history of CAD	0=no, 1=yes	Family Hx Premature CAD Direct Relatives: Family history includes any direct blood relatives (parents, siblings, children) who have had any of the following diagnosed at age less than 55 years for male relatives or less than 65 years for female relatives: A. Angina B. Acute myocardial infarction C. Sudden cardiac death without obvious cause D. Coronary artery bypass graft surgery E. Percutaneous coronary intervention

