		
exertional or NOT otherwise consistent with pain or discomfort of myocardial ischemic origin. This includes patients with non-cardiac pain (for example, pulmonary embolism, musculoskeletal, or esophageal discomfort), or cardiac pain not caused by myocardial ischemia (for example, acute pericarditis).
 
3. Stable angina: Angina without a change in frequency or pattern for the 6 weeks prior to this cath lab visit. Angina is controlled by rest and/or oral or transcutaneous medications
 
4. Unstable angina: There are three principal presentations of unstable angina:
 
 a. Rest angina (occurring at rest and prolonged, usually >20 minutes) b. New onset angina (within the past 2 months, of at least Canadian Cardiovascular Society Class III severity); or c. Increasing angina (previously diagnosed angina that has become distinctly more frequent, longer in duration, or increased by 1 or more Canadian Cardiovascular Society class to at least CCS III severity). 
5. Non-STEMI: The patient was hospitalized for a non-ST elevation myocardial infarction (STEMI) as documented in the medical record. Non-STEMIs are characterized by the presence of both criteria:
 
 a. Cardiac biomarkers (creatinine kinase-myocardial band, Troponin T or I) exceed the upper limit of normal according to the individual hospital's laboratory parameters with a clinical presentation which is consistent or suggestive of ischemia. ECG changes and/or ischemic

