Procedural ASA	0=no, 1=yes	Indicate if the patient was administered aspirin at any time during index procedure
Procedural Fondaparinux	0=no, 1=yes	Indicate if the patient was administered fondaparinux at any time during index procedure
Procedural LMWH	0=no, 1=yes	Indicate if the patient was administered a lowmolecular heparin at any time during index procedure
Procedural UFH	0=no, 1=yes	Indicate if the patient was administered fondaparinux at any time during index procedure
Procedural Bival	0=no, 1=yes	Indicate if the patient was administered bivalirudin at any time during index procedure
Procedural lib/IIIa	0=no, 1=yes	Indicate if the patient was administered IIb/IIIa inhibitor at any time during index procedure
Clopidogrel loading	0=no, 1=yes	Indicate if the patient was administered a loading dose of clopidogrel

Prasugrel loading	0=no, 1=yes	Indicate if the patient was administered a loading dose of prasugrel
Ticagrelor loading	0=no, 1=yes	Indicate if the patient was administered a loading dose of ticagrelor
Discharge ACE-I or ARB	0=no, 1=yes	At the time of discharge, was the patient prescribed an ACE-Inhibitor (or ARB)
Discharge ASA	0=no, 1=yes	At the time of discharge, was the patient prescribed aspirin
Discharge bbl	0=no, 1=yes	At the time of discharge, was the patient prescribed a beta blocker
Discharge Statin	0=no, 1=yes	At the time of discharge, was the patient prescribed a statin
Discharge Clopidogrel	0=no, 1=yes	At the time of discharge, was the patient prescribed clopidogrel
Discharge Clopidogrel 75 mg	0=no, 1=yes	At the time of discharge, was the patient prescribed clopidogrel 75mg
Discharge Clopidogrel 150 mg	0=no, 1=yes	At the time of discharge, was the patient prescribed clopidogrel 150mg
Discharge Prasugrel	0=no, 1=yes	At the time of discharge, was the patient prescribed prasugrel
Discharge Prasugrel 5mg	0=no, 1=yes	At the time of discharge, was the patient prescribed prasugrel 5mg
Discharge Prasugrel 10mg	0=no, 1=yes	At the time of discharge, was the patient prescribed prasugrel 10mg
Discharge Ticagrelor	0=no, 1=yes	At the time of discharge, was the patient prescribed ticagrelor
Discharge Anticoagulant	0=no, 1=yes	At the time of discharge, was the patient prescribed an anticoagulant (warfarin; LMWH; rivoraxaban)
Multivessel disease	0=no, 1=yes	Value is 1 if number of diseased vessels > 1
Number of lesions treated	##	Total number of lesions treated during the index PCI

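### The data dictionary does not make troponin comparable across the 8 pooled centres, and it defines procedural heparin as fondaparinux, so adjustment through these fields may be incomplete.

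*SAP*

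**What the plan says.** SAP 5.1 pools records "from 8 academic centers in the US". In SAP Section 13 (Attachment 1) the troponin row reads "Troponin Pre-procedure value", with nothing in the value column. Peak troponin is also blank. The neighbouring row reads "CK-MB baseline ng/ml Pre-procedure value". Mock Table 1 in SAP Section 12 repeats the contrast: "Baseline CK-MB, ng/ml" has its unit and the troponin rows have none. Protocol Attachment 1 has the same blanks.

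Under CAD presentation, both attachments allow CK-MB, troponin T or troponin I, and ask that it "exceed the upper limit of normal according to the individual hospital's laboratory parameters".

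SAP 8.1 says that the variables in the Section 12 tables "will be considered as demographic or baseline variables". Table 1 summarises troponin by mean, SD, median, minimum and maximum, with a t-test. For the propensity score, SAP 6.1 states that, besides age and gender, "this model will include all baseline covariates demonstrating significant differences" at p<0.05, plus others by consensus. The covariate-adjusted sensitivity model uses the same threshold. Study centre is a covariate in the outcome Cox model and is not named in the propensity model. The within-stratum balance check covers age, gender, creatinine, hemoglobin and diabetes.

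The heparin field reads "Procedural UFH 0=no, 1=yes Indicate if the patient was administered fondaparinux at any time during index procedure". The protocol has the same text, and fondaparinux has its own field with the same description.

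**The concern.** SAP 6.3 expects significant baseline differences between the drug groups, and the study's stated advantage over claims data is better baseline adjustment. If troponin is related to both drug choice and MACE (an assumption; the documents give no figures), its adjustment matters. A number whose scale may depend on the laboratory can adjust only in part. Three features would let a failure pass unnoticed: entry is decided by a test on the raw pooled value, centre is not named in the propensity model, and troponin is not among the five balance variables.

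The UFH text is a separate matter. A site that follows the written definition records fondaparinux twice and heparin never. The UFH row of Table 2 would then be wrong, and a procedural anticoagulant would be missing from adjustment, including for the bleeding comparisons.

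**Working it through.** The plan states no figure on this point, so the first check is a reading of the fields.

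**1. Units given**

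| Field | SAP Attachment 1 | Protocol Attachment 1 | SAP Table 1 |
|---|---|---|---|
| Creatinine | mg/dl | mg/dl | mg/dl |
| Hemoglobin (pre-procedure) | g/dl | g/dl | mg/dl |
| CK-MB | ng/ml | ng/ml | ng/ml |
| Troponin | none | none | none |
| Peak troponin | none | none | none |

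The troponin blank appears in all three places, so it is unlikely to come from text extraction. The hemoglobin unit in Table 1 also disagrees with the dictionary.

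**2. How easily a field enters.** With 4,303 per group (SAP 6.8), p<0.05 needs a standardized difference of about 1.96 × √(2/4303) = 0.042. Entry is conditional but the bar is low. If mixed scales inflate the SD, a real difference can also be missed.

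**3. What mixed units would do.** Assume half the patients come from centres recording in ng/L and half in ng/mL, with the same true mean m. The pooled mean is 0.5m + 0.5 × 1000m = 500.5m, of which 500/500.5 = 99.9% comes from the ng/L centres. On the log scale, log(k × x) = log k + log x, so a constant scale factor per centre is an additive shift. A centre term absorbs it on the log scale but not on the raw scale.

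**4. Simulation A (all inputs assumed).** 34,424 patients (4 × 8,606), 60 runs, 8 centres. Log10 troponin has SD 1, with treatment log-odds 0.4 and outcome log-hazard 0.3 per SD. The true ratio is 0.80. Four centres record in ng/mL and four in ng/L. Analysis used 5 propensity strata and a Mantel-Haenszel risk ratio.

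| Propensity model | Risk ratio |
|---|---|
| None (crude) | 0.898 |
| Troponin, one unit | 0.812 |
| Troponin, mixed units, no centre | 0.861 |
| Local above/below-limit indicator only | 0.846 |
| Indicator plus mixed-unit troponin | 0.836 |
| Log troponin, mixed units, plus centre | 0.812 |

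Share of the achievable correction kept, on the log scale:
- mixed units: ln(0.898/0.861) / ln(0.898/0.812) = 0.042/0.101 = 42%
- indicator plus mixed units: ln(0.898/0.836) / ln(0.898/0.812) = 0.072/0.101 = 71%

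Residual against the one-unit result: 0.861/0.812 = 1.06 and 0.836/0.812 = 1.03, that is 3-6%. With troponin as the only covariate, strata depend on its rank alone, so raw and log values give the same answer. This simulation therefore cannot show any effect of skewness.

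**5. Simulation B (all inputs assumed).** 80,000 patients, 8 centres, no true effect. Upper limits 0.01-0.5, with or without one centre on a 1,000-fold unit. Troponin log-odds −0.25 to −0.40 per SD on treatment and 0.5 on MACE. Presentation adjusted, decile strata, centre in the outcome model.

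| Troponin in the propensity model | Adjusted OR (true 1.00) |
|---|---|
| None | 0.901-0.938 |
| Raw | 0.938-0.970 |
| Log raw | 0.895-0.940 |
| Multiple of limit | 0.968-0.980 |
| Log multiple of limit | 0.992-0.996 |

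Raw troponin leaves 3-6%. Pairing like ends of the ranges (itself an assumption), it removes ln(0.938/0.901)/−ln(0.901) = 39% to ln(0.970/0.938)/−ln(0.938) = 52% of the bias. Dividing by the limit without logging still leaves ln(0.968)/ln(0.938) = 51% to ln(0.980)/ln(0.970) = 66% of what raw troponin left. That part is skewness, not units.

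A further run on similar assumptions gave 0.95-0.97 with raw troponin, 0.90-0.94 with raw troponin plus centre in the propensity model, and 0.99-1.00 with the log multiple. Centre alone did not rescue the raw value.

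**6. UFH.** Coded by the definition, the UFH and fondaparinux columns are identical. Two identical columns in one model are perfectly collinear, and heparin use is not recoverable. Coded by the field label, nothing is lost.

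**The case against.** The case for leaving this alone is substantial. Troponin and UFH are not on the named covariate list and enter only by p-value or consensus. CAD presentation, judged against each hospital's own limit, carries part of the same information, and the covariate-adjusted model names it. SAP 6.1 requires the baseline data to be reviewed and the outcome analysis fixed before outcomes are examined. Table 1 prints minimum and maximum, where a 1,000-fold mismatch would probably show. The consensus rule leaves room to add centre to the propensity model. SAP 5.2 and 7.1 promise standardized extraction sheets and site instructions. The simulated size also depends on assuming a gross mismatch: one rerun gave raw 0.973 against multiple-of-limit 0.981 without it, and 0.950 against 0.981 with it. The UFH text looks like a copying slip under a correct label, and the data come mainly from existing registry records.

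These points limit the size, and they stand. They do not supply the missing unit or correct the definition. The content of the site instructions is not given, so they neither prove nor exclude a remedy. Smaller assay differences need not show in a minimum or maximum.

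A reader might infer that these fields cannot carry the confounding at all, or that the plan builds in a 3-6% spurious benefit for prasugrel. The documents support neither. Mixed-scale troponin still removed a substantial share of the bias in the simulations above. The two simulations assume opposite directions of confounding, and no passage shows that any centre differs in unit or assay.

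**Conclusion.** The point holds as a gap in the dictionary with a cheap remedy. The documents do not ensure that troponin is comparable across the 8 centres, yet they make its raw pooled value eligible for the propensity and covariate models, so adjustment through it may be incomplete. Size and direction are unknown. The few percent of residual bias, set against a planned 20% reduction, rests wholly on assumed confounding strengths, limits and unit mixes, and part of it comes from skewness. The UFH definition is wrong as written in both attachments; heparin is lost only if sites code by the definition rather than the label. No stated figure of the plan changes.

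**What to change.** 1. Correct the Procedural UFH definition in both attachments to unfractionated heparin, and have each site confirm its mapping before pooling.
2. Obtain troponin unit, assay (T or I) and upper limit from each site by calendar period. The technical instructions promised in SAP 7.1 are a natural place to ask.
3. Use log(troponin/upper limit) in Table 1 and in all models in place of the raw value, or an above/below-limit indicator where only that is known. Both the log and the limit are needed: in simulation B neither alone was enough.
4. Name study centre in the propensity model. On log-scale troponin this absorbs a constant scale difference per centre; it does not replace step 3 for a raw value.

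The cost is a short query to each site, one derived variable and a corrected field definition. If sites mapped UFH by its label, no new patient-level data are needed; a site that coded by the definition would have to extract that field again.
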